7.2 Methods and Timing for Assessing, Recording, and Analyzing Safety Parameters

Assessment of adverse reaction at the post-intervention visit.

7.3 Adverse Events and Serious Adverse Events

An **adverse event (AE)** is generally defined as any unfavorable and unintended diagnosis, symptom, sign (including an abnormal laboratory finding), syndrome or disease which either occurs during the study, having been absent at baseline, or if present at baseline, appears to worsen. Adverse events are to be recorded regardless of their relationship to the study intervention.

A serious adverse event (SAE) is generally defined as any untoward medical occurrence that results in death, is life threatening, requires inpatient hospitalization or prolongation of existing hospitalization, results in persistent or significant disability/incapacity, or is a congenital anomaly.

No serious adverse event out of character with nasal irrigations is expected.

Adverse events captured during interval clinical visit are captured as unsolicited events, but if patient reports by calling PI directly using number on the consent form it will be captured as a solicited event. The events will be recorded as such so that there are no double collection systems.

If there are any adverse events or serious adverse events reported by the patient to the co-investigators at any point post-interventional procedure throughout the study, the Principal Investigator will be notified within 24 hours.

7.4 Reporting Procedures

If there are any adverse events or serious adverse events reported by the patient to the co-investigators at any point (post-interventional procedure) throughout the study, the Principal Investigator will be notified within 24 hours. The co-investigator will record the occurrence in the patient's research file within 24 hours of report of the incident.

Decision of relatedness and severity will be made by the Principle Investigator.

Details of the adverse event will be maintained in the Reportable Event Tracking Log for this study.

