2.2 Study Rationale

The interventional regimen is as follows.

Patient will undergo pre-intervention nasal swab from the affected sinus that will be sent for gram stain and bacterial culture and sensitivities.

If pathogen identified in the bacterial culture is pseudomonas aeruginosa, topical tobramycin or gentamycin will be assigned as first line agent pending culture profiles and cost factors. If the sensitivities show resistance to both tobramycin and gentamycin, then levofloxacin will be prescribed.

If the pathogen identified in the bacterial culture is other than pseudomonas aeruginosa, mupirocin will be prescribed. If the pathogen shows resistance to mupirocin, then the patient will be prescribed one of the other three antibiotics will be prescribed pending culture profiles and cost factors

The patient will use the topical antibiotic twice a day for 28 days. This will be accomplished by first proceeding with their normal nasal rinse regimen as prescribed by their physician (this may include saline alone, or saline with budesonide). Twice per day, at the end of each regimen, they perform one additional nasal saline rinse using the Neil Med sinus rinse bottle in the manner outlined on the packaging instructions. However, with this last additional nasal saline rinse, they will open their antibiotic capsule and drop the contents into the rinse bottle prior to rinsing.

Known and potential risks are as follows:

Potential risks of nasal saline irrigation is stinging sensation and burning Potential risks of filling the nasal saline irrigation rinse bottle with water that is too hot is mucosal burns

Potential risks of topical antibiotic administration include local pruritis and inflammation Potential risks of selection antibiotic resistant organisms. Potential risk for hearing loss

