3 STUDY DESIGN

This is a prospective, pilot study to investigate the presence or absence of antibiotic resistant organisms after treatment of chronic rhinosinusitis with topical antibiotics. In addition, therapeutic effects of the topical antibiotics will be investigated via assessment of patient symptoms, and physical exam endoscopic findings.

There will be 1 study group with 20 patients.

The patients will first undergo pre-intervention assessment in the outpatient setting. This will occur in the Department of Otorhinolaryngology on the 12th floor of the Gonda building in Rochester, MN with one of the staff rhinologists. Patients will be selected to participate if they have active mucopurulence on their endoscopic examination. The assessment will consist of 1) obtaining a nasal swab of mucopurulence from the affected sinus to be sent for gram stain, culture and sensitivity, 2) assessment of patient symptom severity score as measured by the self-administered Sino-Nasal Outcomes Test (SNOT-22) survey, and 3) assessment of patient physical exam as evaluated by rigid nasal endoscopy and documented in Lund-Kennedy endoscopic findings form.

The study intervention is the administration of culture directed topical antibiotics over 28 days. These antibiotics will prescribed to the patient in capsule form as compounded by the Mayo Clinic pharmacy, or suitable licensed compounding pharmacy. One capsule will subsequently be added to a nasal saline irrigation bottle, and the patient will administer this irrigation to him or herself in the usual fashion twice per day.

- The dosages of the antibiotic capsules were determined by the Mayo Clinic pharmacy team with input from infectious disease, based upon available published data, and will be as follows, dissolved in a standard 240mL saline irrigation rinse
 - Mupirocin: 30 mg
 - Tobramycin: 192 mg
 - Gentamicin: 192 mg
 - Levofloxacin: 250mg

After the completion of the study intervention (within 21 days), the patient will undergo post-intervention assessment in the outpatient setting, again in the Department of Otorhinolaryngology with one of the staff rhinologists. The patient will again be assessed with 1) nasal swab from the affected sinus sent for gram stain, culture and sensitivity 2) SNOT-22 symptom scores and 3) Lund-Kennedy endoscopic exam scores.

SELECTION AND ENROLLMENT OF PARTICIPANTS 4

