5.4 Adherence Assessment

Definition of adherence to study intervention will study subject attestation that they completed at least 48 / 56 dosages of nasal saline irrigation with topical antibiotic and presentation for one post-intervention assessment. Patient will record topical antibiotic use in a daily log. This log will be used by the investigators to assess adherence. These available endpoints will be taken and incorporated into analysis.

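### Adverse events are actively assessed only after dosing ends, and the 24-hour reporting rule is unclear for reports made during the 28 days of dosing

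*Combined protocol and SAP*

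**What the plan says.** - **Exposure.** Section 2.2: "The patient will use the topical antibiotic twice a day for 28 days". Section 5.4 sets adherence at having "completed at least 48 / 56 dosages of nasal saline irrigation with topical antibiotic". Patients irrigate at home.
- **Scheduled safety enquiry.** Section 7.2 consists of one line: "Assessment of adverse reaction at the post-intervention visit". Section 3 times that visit: "After the completion of the study intervention (within 21 days), the patient will undergo post-intervention assessment in the outpatient setting". The schedule in 6.1 has a pre-intervention and a post-intervention assessment and no contact between them.
- **What counts as an adverse event.** Section 7.3 covers any unfavourable occurrence "which either occurs during the study, having been absent at baseline, or if present at baseline, appears to worsen", and requires recording whether or not the event is related to treatment.
- **Capture outside the scheduled visit.** Section 7.3 mentions two routes: an interval clinical visit, and a telephone call from the patient to the PI.
- **The 24-hour rule.** In 7.3 the PI must hear within 24 hours of events "reported by the patient to the co-investigators at any point post-interventional procedure throughout the study". Section 7.4 repeats the rule with the qualifier in brackets, "at any point (post-interventional procedure) throughout the study", and adds that the co-investigator enters the occurrence in the research file within 24 hours of the report.
- **Daily log.** Section 5.4: "Patient will record topical antibiotic use in a daily log". Its stated use is to assess adherence; no symptom entry is described.
- **Suspension.** Section 9.3 lists safety findings, including a rise in event frequency, that would pause enrolment or the study intervention.

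**The concern.** The reporting rule reads as if written for a one-time procedure, where everything of interest happens afterwards. Here the intervention is four weeks of self-administered irrigation, so the exposure period itself is when the local risks named in 2.2 (stinging, burns, itching, inflammation) would be expected to appear. Two things follow.

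First, nobody is scheduled to ask about harm while the patient is being exposed. Mild and moderate events, the kind patients tend not to telephone about, are then reconstructed from memory, with uncertain onset dates.

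Secondly, a co-investigator who hears of an event on, say, day 10 cannot tell from the text whether the 24-hour clock applies. Different staff could apply different rules. The suspension rule in 9.3 and the emphasis in section 8 on safety data from patients who stop because of an adverse event both depend on this information arriving in time.

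**Working it through.** **Reproducing the plan's figure.** Inputs: 2 doses per day and 28 days (2.2). 2 × 28 = 56, which matches the denominator in 5.4.

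**Time to the first scheduled enquiry.** Inputs: 28 days of dosing; visit 0 to 21 days after completion (section 3).

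- Earliest: 28 + 0 = day 28 after the start of dosing.
- Latest: 28 + 21 = day 49, and 49 / 7 = 7 weeks.

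**Wait between onset and first enquiry** (visit day minus onset day), for events not volunteered earlier:

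- Onset at the start of dosing: 28 to 49 days.
- Onset on the last dosing day: 28 − 28 = 0 to 49 − 28 = 21 days.
- If onsets are spread evenly over the 28 days (an assumption; mean onset day 14): 28 − 14 = 14 to 49 − 14 = 35 days on average.

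**Reading the qualifier.** The phrase *post-interventional procedure* is not defined. Two readings are possible:

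- *After dosing is complete.* This matches how the protocol uses post-intervention in sections 3, 5.2 and 6.1, each time meaning after the course is finished. A day-10 report to a co-investigator is then outside the 24-hour notification rule. It is also outside the file-entry rule, which refers back to the same occurrence.
- *After the intervention has begun.* This gives more work to the words on either side of the qualifier, which speak of any point and of the whole study. A day-10 report is then inside both rules.

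Other text appears to come from a surgical study: 7.5 speaks of wound cultures and 10.3.3 of deviations during surgery. Carried-over wording is therefore a plausible explanation, though the documents do not say so.

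**Each route during dosing:**

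- Call to the PI: the PI knows at once, so no notification clock is needed. The 24-hour file-entry duty names only the co-investigator, so no entry deadline is stated for this route.
- Interval clinical visit: possible, but none appears in 6.1.
- Report to a co-investigator: inside or outside the 24-hour rules according to the reading chosen.
- Daily log: no symptom entry described.

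**The case against.** A reader might infer that harms arising during dosing carry no reporting duty, or that the 24-hour rule covers only the period after dosing. The documents do not support either. Section 7.3 requires all adverse events during the study to be recorded, and 7.4 requires a tracking log with no time limit. The phrase is ambiguous rather than plainly exclusive. The rule also turns on when an event is reported, not when it occurs: a harm on day 10 first mentioned to a co-investigator at the final visit is covered on either reading.

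A reader might also infer that the suspension rule cannot operate during a patient's course. It can: 9.3 allows unscheduled review and can pause the study intervention, and an event telephoned in or caught at an interval visit could trigger it. What is missing is any scheduled source of such data.

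Three further points are fair. The figure of 56 doses describes the planned course; a patient who stops early will have had fewer. The consent form, which carries the number to call, is not among the pages available, so what patients are told about when to call is unknown. And this is a small single-arm pilot in patients who, under 2.1, would receive topical antibiotics anyway, so heavy safety monitoring would be out of proportion.

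These points limit the claim but do not remove it. Neither route open during dosing is active enquiry, and the wording needs correction whichever reading was intended.

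**Conclusion.** The point holds as a gap in scheduled collection together with an ambiguous rule. The only planned enquiry comes 28 to 49 days after the first dose, following the planned 56 doses. Events not volunteered before then rest on up to seven weeks of recall. On the reading that fits the protocol's own usage, the qualifier in 7.3 and 7.4 leaves reports made to co-investigators during dosing outside both 24-hour duties and conflicts with the adverse event definition in 7.3. On the other reading the intention is sound but not stated.

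The day counts assume a full 28-day course and a visit within the 21-day window; the average waits also assume evenly spread onset. The conclusion depends on neither event rates nor recruitment speed, which the documents do not give. It should be corrected, and the correction is inexpensive.

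**What to change.** Reconcile 7.2, 7.3, 7.4 and 9.3 as follows.

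1. In 7.3 and 7.4, replace the qualifier with an explicit window: from the first dose of study antibiotic through the post-treatment assessment. Apply the 24-hour notification and file-entry rules to reports made to any study team member.
2. Add to the daily log already required by 5.4 a dated column for any new or worse symptom that day (yes or no, with a short description).
3. In 7.2, have the log reviewed at the post-treatment visit and adverse events recorded with onset dates.
4. In 9.3, refer to the same window, so it is clear that events reported during dosing feed the suspension review.

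The column mainly improves onset dating and recall. It does not by itself make reporting prompt, because the log is read at the final visit; prompt reporting comes from item 1 and still depends on patients making contact. The cost is protocol wording, one column on an existing form, more minor events to record and slightly more patient burden. No extra visit, test or staff is needed.

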7.5 Follow-up for Adverse Events

Adverse events involving infection will be followed up with appropriate treatment involving wound cultures, broad spectrum antibiotics, and narrow spectrum once the species is identified. Follow up will continue as needed (acute debilitating event), until resolution for chronic AD from the occurrence of adverse event.

8 INTERVENTION DISCONTINUATION

Participants may withdraw voluntarily from participation in the study at any time and for any reason. Participants should continue to be followed, with their permission, after study intervention has been administered.

Replacement of participants who discontinue early is allowed. The participants who are replaced will not be counted in the study and replacement can occur if participants do not complete the at least 48 / 56 dosages of intervention with topical antibiotics.

It is vital to collect safety data on any subject discontinued due to an AE or SAE. In any case, every effort will be made to undertake protocol-specified safety follow-up procedures. If voluntary withdrawal occurs, the subject will be asked to continue scheduled evaluations, complete an end-of-study evaluation, and be given appropriate care under medical supervision until the symptoms of any AE resolve or the subject's condition becomes stable.

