9.5 Data Analyses

Statistical Methods

Continuous patient characters will be summarized with means and standard deviations for features that are approximately normally distributed and with medians, interquartile ranges, and ranges otherwise. Categorical features will be summarized with frequency counts and percentages.

Primary endpoint:

Number and proportion of patients who developed antibiotic resistance organism will be summarized. 95% confidence intervals will be provided for the proportion.

Secondary endpoint:

1) SNOT-22 symptom scores and Lund-Kennedy endoscopic exam score will be summarized as mean (standard deviation) and median (range).

2). Definition of adherence to study intervention will be to complete 25 of 28 days of topical antibiotics and attend the pre-intervention / enrollment visit as well as the post-intervention assessment visit. Number and proportion of patients with adherence will be reported.

3) Audiometric data will be summarized as a mean (standard deviation) and median (range)

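### Section 8 does not say whether replaced participants stay in the analysis, 9.5 gives no denominators, and 5.4 and 9.5 define adherence differently

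*Combined protocol and SAP*

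**What the plan says.** Section 8 opens its replacement rule with "Replacement of participants who discontinue early is allowed". It continues with "The participants who are replaced will not be counted in the study" and adds that "replacement can occur if participants do not complete the at least 48 / 56 dosages of intervention". It is unclear whether the dose threshold narrows the first sentence to certain early discontinuers or extends replacement to anyone below the threshold. The wording is permissive, so replacement is a choice made case by case. The same section says that after voluntary withdrawal "the subject will be asked to continue scheduled evaluations, complete an end-of-study evaluation", so outcome data may exist for people who are replaced.

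Adherence is a secondary objective in section 1.1 and is analysed in 9.5, although 9.4.2 does not list it as an outcome. Section 5.4 defines it as having "completed at least 48 / 56 dosages of nasal saline irrigation with topical antibiotic", by the participant's own attestation supported by a daily log, plus one post-intervention assessment. Section 9.5 defines it as to "complete 25 of 28 days of topical antibiotics", plus the enrolment and post-intervention visits, and then says: "Number and proportion of patients with adherence will be reported". Section 9.5 also reports the number and proportion of patients who develop a resistant organism, with a 95% confidence interval. It names no analysis set or denominator for either proportion.

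**The concern.** The threshold that permits replacement in section 8 is the threshold that defines adherence in 5.4. If the not-counted clause means exclusion from the analysis, the study would be removing failures from the proportion it sets out to estimate, and the result would no longer describe the patients who were prescribed the rinse. Section 9.2 says the pilot is meant to collect data for a larger study, so an adherence figure that is too high could mislead that design.

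The primary proportion is exposed to the same choice. Whether a patient's culture result enters it would depend on doses taken after baseline and on a discretionary decision to replace.

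Apart from replacement, two adherence definitions are in force for one reported endpoint, so two analysts following the document could report different numbers.

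**Working it through.** The plan gives no adherence, replacement or resistance rate, so there is no stated figure to reproduce beyond the thresholds. The replacement counts below are assumptions.

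**Thresholds.** Section 2.2 specifies use twice a day for 28 days: 2 × 28 = 56 doses, which matches 5.4.
- Section 5.4: 48/56 = 85.7% of doses, equal to 48/2 = 24 full days.
- Section 9.5: 25/28 = 89.3% of days, equal to 25 × 2 = 50 doses if a day means both doses.

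**Do the definitions agree?** Take a day to mean both doses. A patient with k doses (k at least 28) has between k − 28 and k/2 (rounded down) full days. Assuming the visits are attended:

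| Doses taken | Full days possible | 5.4 | 9.5 |
|---|---|---|---|
| 47 or fewer | at most 23 | no | no |
| 48–49 | at most 24 | yes | no |
| 50–52 | 22 to 26, depending on pattern | yes | yes or no |
| 53 or more | at least 25 | yes | yes |

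Disagreement is confined to 48–52 doses and always runs one way: adherent under 5.4, not under 9.5. The simplest case is 24 full days.

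**Effect of leaving replaced patients out, 5.4 rule.** Let N be the number counted, s the number below 48/56 among all treated, and r the number of those replaced and dropped. Assume all post-intervention visits are attended.
- Reported: (N − (s − r))/N.
- Among all treated: (N − (s − r))/(N + r).
- The reported figure is too high by the factor (N + r)/N.

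Sections 3 and 9 give different sizes (20 and 40), which is a separate matter, so both are shown.

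| N | s | r | Reported | All treated |
|---|---|---|---|---|
| 20 | 5 | 0 | 15/20 = 75.0% | 15/20 = 75.0% |
| 20 | 5 | 2 | 17/20 = 85.0% | 17/22 = 77.3% |
| 20 | 5 | 5 | 20/20 = 100% | 20/25 = 80.0% |
| 40 | 10 | 4 | 34/40 = 85.0% | 34/44 = 77.3% |
| 40 | 10 | 10 | 40/40 = 100% | 40/50 = 80.0% |

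**Same check, 9.5 rule.** With a day meaning both doses, everyone below 48 doses has at most 23 full days and is non-adherent under 9.5 too, so dropping them again raises the figure. A patient with 24 full days has 48 doses, is not below the replacement threshold, and is non-adherent under 9.5. If one of the 20 counted patients were such a case and all 5 shortfalls were replaced, the report would be 19/20 = 95.0% against 19/25 = 76.0% of those treated.

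**Resistance.** The documents give no resistance rate for counted or for replaced patients, so neither the direction nor the size of any bias can be calculated.

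**The case against.** The strongest reply is that the not-counted clause means only that replaced participants do not fill a place in the target size. On that reading nothing is distorted. The text allows it but does not say it, and 9.5 does not settle the matter. The conflict between the two adherence definitions remains on either reading.

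It can also be said that this is a descriptive pilot with no test or decision rule, and that a completer analysis is legitimate if it is specified in advance and labelled. Both points stand. They limit the seriousness, and they are the reason a threshold-meeting set can be kept as supportive.

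A reader might infer four stronger things that the documents do not support:
- **That 100% adherence is guaranteed.** This holds only for the 5.4 dose criterion, and only if every shortfall is replaced and dropped. Replacement is optional, and the 9.5 rule does not force it.
- **That resistance will be understated.** Nothing in the documents says how replaced patients differ in resistance, and the effect may be nil.
- **That 5.4 and 10.3.3 are opposing analysis-set rules.** The closing sentence of 5.4, "These available endpoints will be taken and incorporated into analysis", follows text on the dose log and most naturally refers to adherence data. Section 10.3.3 limits the data used to those that conform to the protocol, but it concerns deviations, and nothing says missed doses are a deviation. Both are weak evidence either way.
- **That 9.5 would accept a patient who took about half the doses.** This requires a single dose to complete a twice-daily day, the least natural reading. It would also let a patient below 48 doses be adherent under 9.5, so the upward direction shown for 9.5 assumes that a day means both doses.

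**Conclusion.** The point holds as a conditional bias and an unconditional contradiction; it should be fixed. If replaced participants are left out of the analysis, reported adherence is inflated by the factor (N + r)/N whenever the r patients dropped are non-adherent. In the partial-replacement illustration this is 85.0% against 77.3%, and at the extreme 100% against 80.0%. These figures rest on assumed counts, the 5.4 rule and full attendance at post-intervention visits. Under 9.5 the direction is the same if a day means both doses, but 100% is not built in. If the clause concerns the target size only, this bias is absent. For resistance, the defect is that inclusion may depend on a discretionary post-baseline choice; no size can be put on it.

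The conflict between 48/56 doses and 25/28 days needs no assumption about replacement. If a day means both doses, some patients with 48–52 doses are classified differently.

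**What to change.** - **Section 8:** keep replacement, but state that replaced participants do not count towards the target size and remain in the analysis and safety summaries. State whether the dose-threshold sentence applies only to early discontinuers. List all replacements with reasons.
- **Section 9.5:** report adherence among all participants prescribed study drug. Report resistance among all who took at least one dose and have a post-treatment culture result, and show the number without a result and the reasons. Present the set meeting the adherence threshold as supportive.
- **Sections 5.4, 8 and 9.5:** reconcile to one adherence definition taken from the daily log. If it is in days, say what counts as a day.
- **Section 10.3.3:** reword so that it cannot be read as excluding these patients.

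The cost is wording in four sections and a list of replacements. No visits are added, because section 8 already asks participants who withdraw to continue evaluations. The downside is that the reported adherence figure may be less favourable.
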